**Phase 2:**

- Participants aged 18-64 and 65-85 years.
- 8 groups enrolled in parallel (3 mRNA groups and 1 control group for each age range), [Table 7](#).
- Approximate number of participants: **960 (120** participants per group).
- Blinding: observer-blind. Refer to Section [6.4](#) for more information on blinding.
- **CCI**  
[REDACTED]  
[REDACTED]

Table 7 List of study interventions for Phase 2

Study groups	Study interventions*	CCI
Flu mRNA_Ph2_1_YA	F2F23D/DL001Z-NH	
Flu mRNA_Ph2_2_YA	F2F23A/DL001Z-NH	
Flu mRNA_Ph2_3_YA	F2F23B/DL001Z-NH	
Control_Ph2_YA	CCI	Refer to Table 9 for details
Flu mRNA_Ph2_1_OA	F2F23A/DL001Z-NH	CCI
Flu mRNA_Ph2_2_OA	F2F23B/DL001Z-NH	
Flu mRNA_Ph2_3_OA	F2F23C/DL001Z-NH	
Control_Ph2_OA	CCI	Refer to Table 9 for details

CCI

YA: younger adult; OA: older adult.

\* Strains used to design study interventions are based on WHO recommendation for influenza virus vaccine composition for the 2023-2024 NH season.

\*\* CCI : GSKVx000000048110; CCI : GSKVx000000040033; CCI  
GSKVx000000034794; CCI : GSKVx000000034795; CCI GSKVx000000048111; CCI : GSKVx000000034797; CCI : GSKVx000000034798; CCI  
GSKVx000000039711. Refer to Section 4.3.2 for additional information and Section 6.1 for details on study interventions.

Note: CCI

.

- Study interventions in Phase 2 will be provided to the site staff/pharmacist in vials containing the CCI [REDACTED], that will be reconstituted with diluent according to the instructions detailed in Pharmacy Manual, prior to dosing the participants.

#### *Study extension*

***Participants who complete the Phase 2 part of the study will be offered an opportunity to participate in the extension study (FLU SV mRNA-019).***

#### **4.2. Scientific rationale for study design**

The study objective is to generate Phase 1/2 reactogenicity, safety, immunogenicity, and dose-finding/dose-confirming data of an mRNA-based CCI [REDACTED] seasonal influenza vaccine candidate in healthy YA and OAs CCI [REDACTED]  
[REDACTED]

##### **4.2.1. Rationale for study design of Phase 1**

Phase 1 will assess the reactogenicity, safety and immunogenicity of 12 different formulations and 1 active control to CCI [REDACTED]  
[REDACTED]  
[REDACTED]  
[REDACTED]  
[REDACTED]  
[REDACTED]  
[REDACTED]

The specific aims for Phase 1 (in YAs only) are:  
CCI [REDACTED]

To minimize the number of study groups and number of healthy participants exposed to suboptimal investigational study intervention formulations, the aims of Phase 1 will be investigated using both CCI [REDACTED]  
[REDACTED]

[REDACTED] In addition to addressing the specific aims above, this design will CCI [REDACTED]  
[REDACTED]  
[REDACTED]  
[REDACTED]

CCI

The Phase 1 part will be conducted in YAs only as the pattern (in contrast to the magnitude) of immune responses against subtype A and B lineage strains observed in CCI was comparable between YAs and OAs (refer to IB for details). The findings in Phase 1 for YAs will therefore be applied to both YA and OA groups in Phase 2.

In Phase 1, all study groups will be enrolled in parallel. Given the careful dose escalation conducted in the FLU SV mRNA-003 (217895) and CV2 SARS-COV2-012 BST (218595) studies and the total dose in all study groups will remain below the maximum tolerated dose identified in these studies (refer to Section 4.3.1 for details on dose justification in Phase 1), employing parallel enrolment is considered appropriate.

Comprehensive safety monitoring will be carried out to ensure the safety and wellbeing of the participants (refer to Section 8.3.7 for details). The safety monitoring in Phase 1 includes, but not limited to (1) screening visit, (2) safety laboratory assessment at screening, Day 1, Day 8 and Day 29, (3) inclusion of sentinel participants and review of safety data prior to dosing non-sentinel participants, (4) per site, an interval of at least 60 minutes between dosing of sentinel participants, (5) all participants will be observed on site for a minimum of 60 minutes after dosing, (6) study holding rules, (7) per site, limitation of maximum number of participants dosed per day, (8) across sites, limitation of maximum number of sentinel participants dosed per day and (9) unblinded review of safety data by *SRT*.

#### 4.2.2. Rationale for study design of Phase 2

Phase 2 will assess the reactogenicity, safety and immunogenicity of 3 different CCI CCI . Given the high unmet need for an improved vaccine in OAs, the Phase 2 part will be conducted in both YAs and OAs to confirm that the selected formulation(s) induces an appropriate immune response in both age groups.

All YA and OA study groups are planned to be enrolled in parallel. Given the

- a. Safety and reactogenicity data from YAs in the Phase 1 part CCI , and
- b. Safety and reactogenicity data in YA and OA from the FLU SV mRNA-003 (217895) and (CV2 SARS-COV2-012 BST [218595]) studies, and
- c. Total dose in all study groups will remain below the maximum dose *evaluated* in Phase 1 CCI ), and
- d. mRNA-based vaccines are less reactogenic in OAs than in YAs supported by both internal (FLU SV mRNA-003 [217895] and CV2 SARS-COV2-012 BST [218595]) and external studies for COVID-19 [Baden, 2021; Polack, 2020] and influenza [Moderna, 2021], employing parallel enrollment and including OAs are considered

appropriate. Refer to IB for details for the safety and reactogenicity data and the maximum tolerated dose.

To ensure the safety and wellbeing of the participants, comprehensive safety monitoring will be carried out (refer to Section 8.3.7 for details). The safety monitoring includes, but not limited to (1) all participants will be observed on site after dosing (for a minimum of 60 minutes for OAs and 30 minutes for YAs), (2) inclusion of sentinel participants in OA groups and review of safety data prior to dosing non-sentinel participants, (3) study holding rules, (4) per site, limitation of maximum number of participants dosed per day in OA groups, (5) across sites, limitation of maximum number of sentinel participants dosed per day in OA groups and (6) review of safety data by **SRT** (blinded) and iSRC (unblinded).

Screening visit and safety laboratory assessment will not be included in the Phase 2 part given the accumulation of safety data from the Phase 1 part of the study (312 participants planned to be enrolled) and from the FLU SV mRNA-003 (217895) and CV2 SARS-COV2-012 BST (218595) studies.

#### **4.2.3. Rationale for choice of study population and choice of comparator**

In this study, participants will be enrolled according to the following age categories:

- Phase 1: 18 to 50 years of age (YAs)
- Phase 2: 18-64 (YA) and 65-85 years of age (OA).

In Phase 1, the target population in the YA groups will be limited to 18 to 50 years of age. In Phase 2, the target population in the YA groups will be 18 to 64 years of age and 65 to 85 years of age in the OA groups. This design will facilitate the generation of additional safety data of the platform **CCI** [REDACTED] in a restricted age range prior to expansion to the full target age range for the vaccine candidate. The division of YAs and OAs at 65 years of age is in alignment with the definitions from WHO and CDC [WHO, 2018; CDC, 2022] and several licensed influenza vaccines.

The comparator in Phase 1 is a licensed influenza vaccine approved for use in persons 18 years of age or older. **CCI** [REDACTED]

[REDACTED]. Refer to Section 6.1 for the details on comparator.

#### **4.3. Justification for dose**

For all dose levels in Phase 1, the total dose will remain below the maximum tolerated dose identified **CCI** [REDACTED] based on the results of the FLU SV mRNA-003 **CCI** [REDACTED] and CV2 SARS-COV2-012 BST **CCI** [REDACTED] studies using the same mRNA backbone and modified nucleotides (Refer to Section 2.1 and IB for details).

**For all dose levels in Phase 2, the total dose will remain below the maximum dose evaluated in YAs in the Phase 1 part [REDACTED]  
(Refer to IB for details).**

#### 4.3.1. Dose selection for Phase 1

The individual dose level of the mRNAs encoding [REDACTED] is based primarily on the immunogenicity data from the FLU SV mRNA-003 (217895) study and secondarily on the [REDACTED] study.

Specifically, [REDACTED] was selected for comparison based on the findings in FLU SV mRNA-003 (217895) where this dose level induced a superior immune response compared to the active control.

The dose range [REDACTED] was selected based on the findings in FLU SV mRNA-003 (217895) and [REDACTED]  
[REDACTED]  
[REDACTED]  
[REDACTED]  
[REDACTED]

For mRNAs encoding [REDACTED] only data from [REDACTED] is available which indicated that NA antigens may need relatively [REDACTED]. However, as the relevance of data generated with [REDACTED] is not completely clear a [REDACTED] was selected to provide a sufficiently broad dose range for these antigens.

Refer to Section 2.1 and IB for details on the FLU SV mRNA-003 (217895) and [REDACTED] studies.

#### 4.3.2. Dose selection for Phase 2

*The individual dose level of the mRNAs encoding [REDACTED] are based primarily on the immunogenicity and safety data from the Phase 1 part of this study and secondarily on the FLU SV mRNA-003 (217895) study.*

*YA dose selection:*

*The lowest total dose level evaluated in [REDACTED] was selected as the maximum dose level for the Phase 2 part in YAs as:*

[REDACTED]

CCI

Considering that a CCI [REDACTED] as compared to the active control, CCI [REDACTED] for the Phase 2 part. The CCI [REDACTED] were selected as:

CCI

*OA dose selection:*

The CCI [REDACTED] was selected as the highest dose level for the Phase 2 part in OAs as:

- mRNA-based vaccines are less immunogenic and reactogenic in OAs than in YAs, as supported by both internal (FLU SV mRNA-003 [217895] and CV2 SARS-COV2-012 BST [218595]) and external studies for COVID-19 [Baden, 2021; Polack, 2020] and influenza [Moderna, 2021], and
- No safety signal has been observed in (i) the Phase 1 part of this study CCI [REDACTED] [REDACTED] and
- A dose level CCI [REDACTED] [REDACTED]
- Dose levels in the Phase 1 part of this study in YA CCI [REDACTED] [REDACTED] [REDACTED] immune responses in OAs.

The YA dose levels CCI [REDACTED] with an optimal immunogenicity/reactogenicity profile in OAs. Further, the lowest dose selected in OAs CCI [REDACTED]

*Refer to the IB for details on the results from the Phase 1 part of this study as well as from the FLU SV mRNA-003 (217895) and CV2 SARS-COV2-012 BST (218595) studies.*

#### **4.4. End of study definition**

A participant is considered to have completed the study if the participant has completed all periods of the study including the last visit or the last scheduled procedure shown in the SoA.

End of Study (EoS) is defined as: LSLV (Visit 6 in Phase 2 part) or Date of the last testing/reading released of the Human Biological Samples, related to primary and secondary endpoints, whichever occurs later. EoS must be achieved no later than 8 months after LSLV. EoS cannot be before LSLV.

### **5. STUDY POPULATION**

Prospective approval of protocol deviations to recruitment and enrollment criteria, also known as protocol waivers or exemptions, is not permitted.

#### **5.1. Inclusion criteria**

Participants are eligible to be included in the study only if all of the following criteria apply:

1. A male or female between and including 18 and 50 years of age in Phase 1 and between and including 18 and 85 years of age (YA: 18-64; OA: 65-85) in Phase 2 at the time of the study intervention administration.
2. Healthy participants or medically stable patients as established by medical history, clinical examination and safety laboratory assessments. Participants with chronic medical conditions with or without specific treatment (e.g., chronic metabolic, cardiac, pulmonary, renal, hepatic, neurologic, and hematologic diseases) are allowed to participate in this study if considered by the investigator as medically stable. A stable medical condition is defined as disease not requiring significant change in therapy or hospitalization for worsening disease during 3 months before enrollment.
3. Body mass index (BMI)  $\geq 18 \text{ kg/m}^2$  and  $\leq 35 \text{ kg/m}^2$ .
4. Participants who, in the opinion of the investigator, can and will comply with the requirements of the protocol (e.g., completion of the eDiary, return for follow up visits).
5. Written informed consent obtained from the participant prior to performing any study-specific procedure.
6. Female participants of non-childbearing potential may be enrolled in the study. Refer to Section [10.4.1.2](#) for the definition of women of non-childbearing potential.

7. Female participants of childbearing potential may be enrolled in the study if the participant:
  - has practiced adequate contraception for 28 days prior to study intervention administration, and
  - has a negative pregnancy test on the day of study intervention administration, and
  - has agreed to continue adequate contraception for at least 1 month after study intervention administration. Refer to Section 10.4 for the definition of women of childbearing potential and adequate contraception.

## 5.2. Exclusion criteria

Participants are excluded from the study if any of the following criteria apply:

### 5.2.1. Medical conditions

1. Only in **Phase 1**: Any clinically significant\* hematological, biochemical, urinalysis or HbA1c laboratory abnormality.

*\*The investigator should use his/her clinical judgment to decide which abnormalities are clinically significant.*
2. Participant tested positive for influenza by local health authority-approved testing methods within 180 days prior to Day 1.
3. Current or past malignancy, unless completely resolved without clinically significant sequelae (e.g., scars following surgical resection for treatment of basal cell carcinoma cases are allowed) for >5 years.
4. Any confirmed or suspected immunosuppressive or immunodeficient condition, including HIV infection, based on medical history and physical examination (no laboratory testing required). However, in **Phase 2**, HIV-infected individuals may be enrolled if they have been stable on antiretroviral therapy for the past 6 consecutive months, i.e., their treatment has not been modified, their CD4 cell count is  $\geq 200/\text{mm}^3$  and their viral load has been undetectable (i.e., HIV-RNA <50 copies/mL) (based on medical records, no laboratory testing required). ***For country specific instruction please refer to Section 10.6.***
5. History of myocarditis or pericarditis less than or equal to 10 years prior to vaccine administration, including a history of myocarditis or pericarditis following vaccination with an mRNA COVID-19 vaccine.
6. Participants with history of hypersensitivity or severe allergic reaction to any previous vaccine or hypersensitivity likely to be exacerbated by any component of the study intervention (including latex, polyethylene glycol, egg protein and aminoglycoside antibiotics).
7. History of, or uncontrolled neurological disorders or seizures, including Guillain-Barré syndrome and Bell's palsy, with the exception of febrile seizures during childhood.

8. Any history of dementia or any medical condition that moderately or severely impairs cognition.
9. Any medical condition that in the judgment of the investigator would make intramuscular injection unsafe.
10. Any other clinical condition that, in the opinion of the investigator, might pose additional risk to the participant due to participation in the study.

### 5.2.2. Prior/Concomitant therapy

11. Administration of an influenza vaccine (including any of the study investigational vaccines) within 180 days before enrollment or planned administration within 28 days (Day 29) after the study intervention administration.
12. **Phase 1:** Administration of a vaccine not foreseen by the study protocol in the period starting 28 days (Day -28) before the study intervention administration, or planned administration within 28 days (Day 29) after the study intervention administration\*.  
**Phase 2: Administration of a vaccine not foreseen by the study protocol in the period starting 15 days (Day -15) before the study intervention administration, or planned administration within 28 days (Day 29) after the study intervention administration\*.**  
*\*In case emergency mass vaccination for an unforeseen public health threat (e.g., a pandemic) is recommended and/or organized by public health authorities outside the routine immunization program, the time period described above can be reduced to 7 days if, necessary for that vaccine, provided it is used according to the local governmental recommendations and that the Sponsor is notified accordingly.*
13. Use of any investigational or non-registered product (drug, vaccine or invasive medical device) other than the study intervention during the period beginning 30 days before the study intervention administration, or their planned use during the study period.
14. Administration of long-acting immune-modifying drugs within 90 days before enrollment or planned use at any time during the study period (e.g., infliximab).
15. Administration of immunoglobulins and/or any blood products or plasma derivatives during the period starting 90 days before the study intervention administration, or planned administration during the study period. Administration of monoclonal antibodies specifically directed against the spike protein of Severe Acute Respiratory Syndrome Coronavirus 2 (SARS-CoV-2), for treatment of COVID-19 disease is allowed.
16. Chronic administration (defined as more than 14 days in total) of immunosuppressants or other immune-modifying drugs during the period starting 3 months prior to the study intervention administration. For corticosteroids, this will mean prednisone equivalent  $\geq 20$  mg/day. Inhaled, topical and intraarticular steroids are allowed.

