## CONFIDENTIAL

217884 (FLU SV mRNA-002)  
Protocol Amendment 2 Final

Type Of Contact	Visit 1	Visit 2*	Contact 1**	Contact 2	Visit 3†	Visit 4	Visit 5‡	Visit 6‡	Notes
Timepoints	Day 1	Day 2	Day 2	Day 3	Day 8	Day 29	Day 92	Day 183	
Recording of SAEs related to study participation, or to a concurrent GSK medication/vaccine	●	●	●	●	●	●	●	●	See Section 8.4.1 for details
Record AEs leading to withdrawal from study	●	●	●	●	●	●	●	●	See Section 8.4.1 for details
Recording of non-serious adverse events	●	●	●	●	●	●			See Section 8.4.1 for details
Recording of MAEs, SAEs, AESIs and pregnancies	●	●	●	●	●	●	●	●	See Section 8.4.1 for details
Record any concomitant medications	●	●	●	●	●	●	●	●	See Section 6.9 for details
Record any intercurrent medical conditions	●	●	●	●	●	●	●	●	See Section 9.2 for details
Study conclusion								●	See Section 10.1.10 for details

● Is used to indicate a study procedure that requires documentation in the individual CRF/eCRF

○ Is used to indicate a study procedure that does not require documentation in the individual CRF/eCRF

† Is used to indicate a study procedure to be performed prior to study intervention administration.

‡ Is used to indicate a study procedure recorded in eDiary.

\* Visit 2 (Day 2) will only be applicable for participants in the exploratory immunogenicity subset in Phase 2. Remaining Phase 2 participants will not have a visit at Day 2.

\*\* Contact 1 (Day 2) will only be applicable for the sentinel OA participants in Phase 2. Remaining Phase 2 participants will not have a contact at Day 2.

\*\*\* Blood samples should only be collected for participants who did not receive a standard of care vaccination against seasonal flu since their enrollment into the study.

† Visit 3 (Day 8) will be replaced by a Contact for all non-subset participants in Phase 2 and if participant did not report any adverse events that would require physical examination on site.

‡ Visit 5 and 6 will be replaced by a Contact if participant has received the standard of care vaccination against seasonal flu after Day 29 and prior to this visit and did not report any adverse events that would require physical examination on site.

Contact may be via telephone, SMS, email, video-telephone/telemedicine or other means, depending on local best practice.

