**Table 3 Intervals between study visits. Phase 1**

Interval*	Planned visit interval	Allowed interval range
Screening Visit** → Visit 1	1-28 days	1 – 28 days
Visit 1 → Contact 1***	1 day	1 day
Visit 1 → Contact 2	2 days	2-3 days
Visit 1 → Visit 2	7 days	6-8 days
Visit 1 → Visit 3	28 days	28-35 days
Visit 1 → Visit 4‡	91 days	84-98 days
Visit 1 → Visit 5‡	182 days	180-210 days

\* Interval is computed as the difference between 2 dates

\*\* Screening Visit is planned for participants enrolled in Phase 1 and needs to be performed within 28 days before Visit 1, with sufficient time to receive/review the hematology, biochemistry, HbA1c and urinalysis results. When applicable, a re-screening visit (including blood and urine sample collection, physical examination and re-checking of inclusion/exclusion criteria) may be scheduled at any time (but only once to assess eligibility) before Visit 1. In this case, all screening procedures must be completed within 28 days before Visit 1 (Day 1). Only laboratory results from the re-screening visit, if it occurs, will be taken into consideration. The participant can only be randomized once the investigator receives the results and confirms the eligibility criteria.

\*\*\* Contact 1 (Day 2) will only be applicable for the sentinel participants in Phase 1. Remaining Phase 1 participants will not have a visit or contact at Day 2.

‡ Visit 4 and 5 will be replaced by a Contact if participant has received the standard of care vaccination against seasonal flu after Day 29 and prior to this visit and did not report any adverse events that would require physical examination on site.

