**Table 4 Intervals between study visits. Phase 2**

Interval*	Planned visit interval	Allowed interval range
Visit 1 → Visit 2**	1 day	1 day
Visit 1 → Contact 1***	1 day	1 day
Visit 1 → Contact 2	2 days	2-3 days
Visit 1 → Visit 3†	7 days	6-8 days
Visit 1 → Visit 4	28 days	28-35 days
Visit 1 → Visit 5‡	91 days	84-98 days
Visit 1 → Visit 6‡	182 days	180-210 days

\* Interval is computed as the difference between 2 dates

\*\* Visit 2 (Day 2) will only be applicable for participants in the exploratory immunogenicity subset in Phase 2.

Remaining Phase 2 participants will not have a visit at Day 2.

\*\*\* Contact 1 (Day 2) will only be applicable for the sentinel OA participants in Phase 2. Remaining Phase 2 participants will not have a contact at Day 2.

† Visit 3 (Day 8) will be replaced by a Contact for all non-subset participants in Phase 2 and if participant did not report any adverse events that would require physical examination on site.

‡ Visit 5 and 6 will be replaced by a Contact if participant has received the standard of care vaccination against seasonal flu after Day 29 and prior to this visit and did not report any adverse events that would require physical examination on site.

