3. ANALYSIS SETS

Analysis Set	Definition / Criteria	Analyses Evaluated
Screened	All participants who were screened for eligibility.	Screening failure
Enrolled	All participants who entered the study (who were randomized or received study intervention or underwent a post-screening study procedure). Note: screening failures (who never passed screening, even if rescreened) and participants screened but never enrolled into the study (met eligibility but not needed) are excluded from the Enrolled analysis set as they did not enter the study.	Study population
Exposed Set (ES)	All participants who received a study intervention. Analysis per group is based on the study intervention administered.	Safety, immunogenicity if applicable, demography
Per Protocol Set (PPS)	All eligible participants who received the dose of study intervention as per protocol, had immunogenicity results pre- and Day 29 post-dosing for at least one CCI [REDACTED], without intercurrent conditions (influenza disease, new malignancy and immunocompromised condition) that may interfere with immunogenicity and without prohibited concomitant medication/vaccination before Day 29. The analysis will be done according to the study intervention that participants received. Results from blood sample deviating from the dosing/blood draw intervals (refer to Table 9 and Table 10) as well as results obtained after intercurrent conditions (influenza disease, new malignancy and immunocompromised condition) that may interfere with immunogenicity or after prohibited concomitant medication/vaccination during this period will be excluded from the PPS.	Immunogenicity, demography

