6.1.4. Protocol Deviations

Important protocol deviations are a subset of protocol deviations (PDs) that may significantly impact the completeness, accuracy, or reliability of the study data or that may significantly affect a participant's rights, safety, or well-being. Important PD rules will be developed and finalized before database lock.

Important PDs include, but are not limited to, the following:

All participant data is excluded from the PPS:

- Study intervention not administered at all
- Invalid/missing informed consent
- Fraudulent data
- Participants got dosed but not as per protocol
- Study intervention storage temperature deviation which is not accepted by quality
- Expired study intervention administered

- Ineligible participant
- Participants randomized using the wrong stratification factor (incorrect age group)

Participant data collected on the day or after the event is excluded from the PPS:

- Influenza disease infection, new malignancy and immunocompromised condition
- Administration of concomitant vaccine(s) forbidden in the protocol
- Administration of any medication forbidden by the protocol, namely administration during the study period of investigational or non-registered product (drug, vaccine or invasive medical device) other than the study intervention, of long-acting immune-modifying drugs or of immunoglobulins and/or any blood products or plasma derivatives with the exception of monoclonal antibodies specifically directed against the spike protein of SARS-CoV-2 virus, for treatment of COVID-19 disease.

Participant lab data collected on the day of the event is excluded from the PPS:

- Participants did not comply with blood sample schedule (see [Table 9](#) and [Table 10](#))
- **CCI** [REDACTED]
- Serological results available but results unreliable (e.g., wrong blood sample management)

The number of participants with important protocol deviations will be summarized by study group across time points and at Day 28 and Day 183. Important protocol deviations will be listed with date of occurrence, deviation description, and analysis set from which participant is excluded. Important protocol deviation summary will be based on the Enrolled Set.

The important PDs will be reported in the Clinical Study Report (CSR). The important PDs leading to elimination from the PPS will be summarized for the ES and the important PDs leading to elimination from the ES will be summarized for the Enrolled Set.

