6.2.1.8. Study Day

Study day will be calculated as follows:

- Study day prior to dosing will be calculated as: date of assessment – date of the study intervention administration
- Study day on or after the date of the dosing will be calculated as: date of assessment – date of the study intervention administration + 1.

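### A licensed flu vaccine given from Day 30 is not prohibited, yet the co-primary Day 29 sample may be drawn up to Day 36, and no stated rule removes a titre taken after it

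*Protocol*

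**What the plan says.** **Restriction on vaccines.** Exclusion criterion 11 (Protocol 5.2.2) covers influenza vaccine "within 180 days before enrollment or planned administration within 28 days (Day 29) after the study intervention administration". Criterion 12 gives other vaccines the same end point in both phases: "or planned administration within 28 days (Day 29) after the study intervention administration".

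**Sampling window.** Protocol Table 3 (Phase 1) has "Visit 1 → Visit 3 28 days 28-35 days", and Protocol Table 4 (Phase 2) has "Visit 1 → Visit 4 28 days 28-35 days". These visits supply the co-primary Day 29 sample.

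**Sampling after a licensed flu vaccine.** A footnote to the schedules of activities in Protocol 1.3 reads "Blood samples should only be collected for participants who did not receive a standard of care vaccination against seasonal flu since their enrollment". It is attached to the Day 92 and Day 183 samples. The Day 29 antibody sample does not carry it in Table 1, Table 2 or the blood-volume table (Table 10). The visit footnotes show that standard-of-care flu vaccination after Day 29 is expected.

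**Analysis rules.** Protocol 9.2 and SAP 3 define the PPS as participants "without prohibited concomitant medication/vaccination before Day 29", among other conditions. SAP 6.1.4 removes data from the day of the event onward for "Administration of concomitant vaccine(s) forbidden in the protocol". SAP Table 2 (Section 1.1.1) lists as an intercurrent event a prohibited medicine or vaccine taken ahead of the Day 29 draw, and excludes the data that follow.

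**Recording.** Protocol 6.9 asks for influenza vaccines to be recorded up to Day 183, and for other vaccines only until Day 28.

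**The concern.** The restriction and the sampling window end on different days. The analysis rules are tied to the restriction, not to the draw. Take a participant who receives the season's licensed flu vaccine on Day 30 and attends on Day 36. The vaccine was allowed and the sample is in window, so the titre is analysed as the response to the study vaccine.

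Day 29 GMT, GMI, SCR and SPR are the co-primary immunogenicity measures. A titre raised by a second influenza vaccine does not measure what those endpoints describe. The plan already treats such samples as not worth collecting at Day 92 and Day 183, and nothing explains why Day 29 differs.

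The situation is foreseeable. Phase 2 uses 2023–2024 northern-hemisphere strains under an amendment dated 28 August 2023. My inference is that some northern sites would reach Day 30–36 during the vaccination season.

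**Working it through.** **1. The plan's own precision figure.** SAP 5.2 gives 108 evaluable participants per group and a log10 SD of 0.5. The half-width of the 95% CI for the GMT ratio is 10^(1.96 × 0.5 × √(2/108)) = 10^0.1334 = 1.359. This reproduces the stated 1.36-fold, which serves below as the yardstick. The gap itself rests on dates.

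**2. The dates.** SAP 6.2.1.8 sets the study day on or after dosing as "date of assessment – date of the study intervention administration + 1".
- Last restricted day: 28 + 1 = Day 29.
- Draw window: 28 + 1 = Day 29 to 35 + 1 = Day 36.
- Days on which a vaccine is allowed and an in-window draw can still follow or coincide: Day 30 to Day 36.
- Longest interval from an allowed vaccine to an in-window draw: 36 − 30 = 6 days.

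**3. Each rule applied to a vaccine on Day 30 and a draw on Day 36.**

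| Rule | Removes the titre? | Why not |
|---|---|---|
| Exclusions 11 and 12 | No | End at Day 29 |
| Visit window | No | Day 36 is in window |
| Do-not-sample footnote | No | Marked for Day 92 and Day 183 only |
| PPS, Protocol 9.2 and SAP 3 | No | Prohibited vaccination only, before Day 29 |
| PPS, result-level sentence | No | Prohibited vaccination only |
| SAP 6.1.4 | No | Forbidden vaccines only |
| SAP Table 2 intercurrent event | No | Runs to the draw, but prohibited vaccination only |

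**4. Size within one group.** If a share f of a group has titres raised r-fold, its GMT is multiplied by r^f. The documents give neither f nor r, so both are assumed.

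| Share f | Of 108 | Boost r | GMT multiplier |
|---|---|---|---|
| 2% | 2.2 | 1.5 | 1.5^0.02 = 1.008 |
| 5% | 5.4 | 2 | 2^0.05 = 1.035 |
| 10% | 10.8 | 3 | 3^0.10 = 1.116 |

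The multiplier is 1 if nobody is vaccinated in the gap.

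**5. Effect on the GMT ratio.** The ratio is multiplied by r_m^f_m / r_c^f_c, where m is the mRNA group and c the control.
- Equal share and equal boost: 1.116 / 1.116 = 1, so there is no bias.
- Extreme one-sided case, with 10% and 3-fold in one arm and none in the other: the ratio moves 1.116-fold. On the log10 scale that is 0.10 × log10(3) = 0.048 against a half-width of 0.133, or about 36% of it.

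**6. Seroconversion.** If a share f is affected and an extra proportion q of those participants seroconvert, the group's SCR rises by 100 × f × q points. For f = 2% and q = 20% that is 0.4 points; for f = 10% and q = 50% it is 5 points. Both q values are assumptions. The between-group difference is unchanged only if both arms gain the same number of points.

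**The case against.** The best counter-argument is that the intent is already visible and the remainder is wording. SAP Table 2 runs its intercurrent event up to the actual draw. The second sentence of the PPS definition removes individual results as well as participants. The SAP 6.1.4 list is expressly not exhaustive, and its rules are to be finalised before database lock. All of that is true. It shows that the team could close the gap, and it rules out saying that such titres are certain to stay in the PPS. But every one of these texts turns on the vaccine being prohibited or forbidden, and an open list does not supply the missing rule.

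A second argument is that the effect is small: at most 6 days for a boost to develop, no hypothesis test, and a wide planned interval. This stands, and it limits the point to a modest one.

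Three stronger readings are tempting, and the documents do not support them:
- **That equal contamination pulls the GMT ratio towards 1.** Step 5 shows that an equal share and equal fold cancel. Attenuation would need a larger boost in the lower-titre arm, and nothing in the documents shows that.
- **That the PPS gap undermines the Phase 2 interim that informs Phase 3.** Protocol 9.4.2 and SAP 4.7 base all interim analyses on the Exposed Set. The same titres would be in that interim, but through a different analysis set, so a PPS edit alone would not reach them.
- **That the protocol bans these vaccines on study and the ban should run longer.** Criteria 11 and 12 are eligibility criteria about planned administration; Protocol 6.9 merely points back to them. How long licensed vaccination is restricted is a clinical matter, and this review proposes no change to it.

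**Conclusion.** The gap is real and present in both phases. An allowed licensed influenza vaccine from Day 30 can precede an in-window co-primary draw by up to 6 days, and the plan as written has no rule that removes the resulting titre. Each group's Day 29 GMT, GMI, SCR and SPR can be inflated. The GMT ratio is biased only if the share vaccinated or the fold boost differs between arms.

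Under assumed shares of 2–10% and boosts of 1.5- to 3-fold, a group's GMT rises by 0.8–11.6%, which is modest beside the 1.36-fold half-width. These inputs are assumptions, and the effect may be nil. The point concerns how the endpoint is defined; the sample size is not in question. It is a cheap improvement, worth making because the affected influenza-vaccine cases can be identified from dates the protocol already records.

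**What to change.** 1. **Protocol 9.2 and SAP 3.** In the PPS definition, where the text reads "without prohibited concomitant medication/vaccination before Day 29", replace the nominal Day 29 with the actual Day 29 blood draw (Visit 3 in Phase 1, Visit 4 in Phase 2). This matches the cut-off in SAP Table 2.
2. **SAP Table 2 and SAP 6.1.4.** Exclude Day 29 and later immunogenicity results collected after any non-study influenza vaccine, whether or not the protocol forbids it, using the influenza vaccine dates recorded to Day 183.
3. **Interim analysis.** Because it uses the Exposed Set, apply the same result-level exclusion to its Day 29 immunogenicity results, or report a sensitivity analysis with it.
4. **Other vaccines.** Reconcile the Day 28 recording limit in Protocol 6.9 with the visit window and with the schedule of activities, which asks about vaccinations at every visit. Until then, the dates needed to handle criterion 12 vaccines are not assured.
5. **Consistency.** Leave the eligibility criteria as they are for this purpose, but note that exclusions 11 and 12, the 28–35 day window and the sampling footnote need to be reconciled.

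The cost is a few phrases across the two documents, plus possibly a few Day 29 results lost from the PPS. Items 1 to 3 need no new data collection for influenza vaccines.
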